5.4 N/A

6.0 Procedures Involved

- 6.1 We will conduct a single-arm, mixed methods feasibility trial design to evaluate the feasibility, acceptability, and preliminary effects of a mindfulness-based intervention ("Growth, Empowerment, and Mindfulness"; GEM) among young adults with early life adversities (n=44), with exploratory analyses of the preliminary outcomes to potentially inform future studies. The GEM intervention is an app-delivered program consisting of weekly learning modules, ecological momentary assessments and interventions (EMA/EMI), and weekly group practice sessions (described in greater detail in Section 5.0 Study Intervention/Investigational Agent). The intervention will offer support for young adults with experiences of early life adversities and its negative behavioral health consequences by helping participants build foundational mindfulness and self-compassion skills, increase interoceptive awareness, reduce experiential avoidance and de-centering, improve emotion regulation and decrease rumination, and integrate mindfulness skills into daily life. GEM is not intended to diagnose, treat, mitigate, or cure any mental health disorder.
- 6.2 Over the study duration of 3-4 months for each participant, we will use a mixed methods, longitudinal design incorporating (1) baseline, (2) post-intervention, and (3) follow-up assessments as well as (4) weekly assessments during the first four weeks of the intervention delivery period ("Recommended Modules") and (5) daily EMAs to evaluate the feasibility, acceptability, and preliminary effects of the GEM program integrating app-based intervention content, weekly group sessions, and EMI delivery. The research team will register and maintain the study information on ClinicalTrials.gov. Specifically, the study PI, with support from the research team members, will be responsible for registering the clinical trial before the enrollment of the first subject, regularly updating study record, posting the IRB-approved informed consent form after the study is closed to recruitment, but no later than 60 days after the last study visit by any

participant, and the timely update of the study materials and results when they become available.

Participant contact: The research team will utilize both email and Avocado (a messaging platform that facilitates text message communication between research staff and study participants without staff member using their personal phone numbers for the study; already vetted by the OIT) when communicating with participants in the study. Access to Avocado inbox used for this study will be limited to necessary study staff. Participants will be asked to indicate their preferred method of contact on the contact form (after consent) and will be contacted only via their selected method.

Baseline (T1), post-intervention (T2), and 3-month follow-up assessments (T3): At each timepoint, participants will complete a Qualtrics survey, which will be accessed through a unique link created based on each participant's deidentified participant identification number (PID).

The Baseline assessment (T1) will include a set of sociodemographic questions as well as a total of 27 scales, measuring depression, anxiety, PTSD, functional impairment due to depression, functional impairment due to anxiety, interoceptive awareness, de-centering, rumination/perseverative thinking, theories of psychological distress, theories of emotion, internalized stigma, emotion regulation, loneliness, mindfulness, self-compassion, perceived stress, political stress, sleep, phone use, early life adversity, childhood trauma, experiences of stress and adversity, everyday experiences of discrimination, rejection sensitivity, Major Depressive Episode, Generalized Anxiety Disorder, and overall well-being (see "Compiled Measures_GEM.docx").

Additionally during the Zoom call for baseline assessment (T1), the RA will "onboard" the participant and (a) review how to use a FitBit, (b) install the study application, and (c) problem solve any logistic issues. The baseline assessment and onboarding will take a total of 90-120 minutes.

The post-intervention assessment (T2) will take place 1-2 weeks after the recommended modules are completed and include a total of 26 scales, measuring depression, anxiety, PTSD, functional impairment due to depression, functional impairment due to anxiety, interoceptive awareness, Major Depressive Episode, Generalized Anxiety Disorder, de-centering, rumination/perseverative thinking, theories of psychological distress, theories of emotion, internalized stigma, emotion regulation, loneliness, mindfulness, self-compassion, perceived stress, political stress, sleep, phone use, applied mindfulness process, overall well-being, client satisfaction, session evaluation, and adverse effects. The post-intervention assessment will take a total of 60-90 minutes.

Additionally at T2, participants will be invited to complete an exit interview via Zoom, the University approved web conferencing platform. Interview will take 90-120 minutes. In line with previous studies from our team, the interview will be recorded using the native recording feature on the Zoom platform (i.e., capturing both video and audio recording) and saved to the interviewer's Brown Zoom cloud. The RA recording the interview will ensure that the setting "Allow cloud recording sharing" is disabled on

Zoom. By disabling this setting, nobody other than the person who made the recording will be able to access that recording on the cloud. Therefore the recording saved to the interviewer's Brown Zoom cloud will be only accessible to the interviewer creating the recording. An audio-only recording file will be downloaded from the Zoom cloud to Stronghold, and the original recording will be deleted from the Brown Zoom cloud.

At follow-up assessment (T3), which will take place 3 months after the baseline assessment, we will include a total of 21 scales, measuring depression, anxiety, PTSD, functional impairment due to depression, functional impairment due to anxiety, Major Depressive Episode, Generalized Anxiety Disorder, interoceptive awareness, de-centering, rumination/perseverative thinking, theories of psychological distress, theories of emotion, internalized stigma, emotion regulation, loneliness, mindfulness, self-compassion, perceived stress, political stress, sleep, phone use, applied mindfulness process, and overall well-being. The follow-up assessment will take a total of 60-90 minutes.

At each of these assessments, participants will join a Zoom meeting with an RA. To mitigate confidentiality risks and risk of third-party participants, The RA will begin the call by instructing participants to complete the procedure in a private location. Participants will be reminded to pause the assessment if another person enters the space. Then, the RA will verbally administer MINI-Major Depressive Episode and MINI-Generalized Anxiety Disorder. Before beginning the MINI modules, RA will remind participants that if they disclose information indicating imminent risk of serious harm to themselves or others, this information must be reported to relevant law enforcement or other authorities. During the assessment, the RAs will have access to a Qualtrics survey with both measures, which will serve as their guide to administer the measures (refer to "Compiled Measures_GEM.docx" for the scale and questions asked). The Qualtrics survey will be accessed only by the RA (i.e., the survey won't be sent directly to the participant) and filled out by the RA as the assessment progresses. The Qualtrics data will only be linked to the participant ID number (deidentified only) and will be kept in a secure location with other de-identified data. After both MINI modules are administered, the participant will be given access the aforementioned unique Qualtrics link to complete the rest of the measures, during which time the participants can ask any questions as they come up during the assessment.

For participants who report suicidality in the MINI-Standard: Major Depressive Episode module, the suicide safety assessment and plan will be followed accordingly (refer to document named "Suicide Safety Plan_GEM.docx and to Section 18.0). Because all eligible participants at this point will have only mild to moderately severe symptoms of depression (individuals with severe symptoms are screened ineligible at the Qualtrics screener survey), there is low likelihood that a participant will be at imminent risk of suicide; however, the suicide safety assessment and plan has been developed out of an abundance of caution. The Suicide Safety Assessment and Plan will be conducted by [name], a licensed psychologist and the principal investigator of the study, or by a study team member who has been formally trained by [name] and

operates under her direct supervision and oversight, consistent with existing clinical trial protocols for NIH-funded studies in the lab. All study personnel will receive training from [name] on identifying and responding to suicide risk. In addition, [name] will be on-call and will be notified immediately of any safety concerns.

Growth, Empowerment, and Mindfulness (GEM) intervention: Participants will complete the intervention through Expiwell, a mobile application native to iOS and Android. The intervention will include 4 weeks of Recommended Modules followed by 2 weeks of Bonus Modules that participants can opt to complete. Each week, participants will gain access to (a) a set of 5-7 'core' modules focused on the topics of early life stress and resilience, environmental stress and disembodied living, experiential avoidance, emotion regulation, mindful self-care, and self-compassion; and (b) 0-4 'optional tailored' modules, specifically on the topics of minority stress and trauma for participants with interest in these topics. On Expiwell, participants will also have access to a list of all mindfulness exercises that have been taught each week. As a meditation-based intervention, the risk of increased psychological distress from meditation (refer to Section 15.1 for more details on foreseeable risks) will also be clearly outlined and communicated in the consent form, and participants will be encouraged to consult with study staff in the case of any increased distress.

In addition to the weekly modules, participants will take part in a weekly, 1-hour "Group practice and connect" session on Zoom. The online sessions will comprise a cohort of 5-10 participants (depending on recruitment) and will be led by a research assistant, who has previous experiences with mindfulness programs as well as lived experiences of early life adversity. During each session, participants will be invited to participate in a group practice and reflection and to join group discussions on experiences regarding past week's practice. In the contact form (which is completed after the consent form), participants will be presented with the day and time of weekly sessions for the next two cohorts and asked to choose the times they are available for. If the participant is not available for either of the offered times, they will be marked as "deferred enrollment" in our participant tracking spreadsheet. A study RA will follow up with information about future cohort scheduling as that information becomes available.

Ecological momentary assessments and interventions: Over the first 4 weeks of the intervention period (i.e., Recommended Modules), participants will also complete 3 EMAs + EMIs per day through Expiwell. EMA and EMI will be delivered concurrently; the EMA will collect participant's response on their current mood, recent stressful experience, and type of stressor; participants will then receive a list of mindfulness exercises, which will be tailored to the type of stressor/emotion they will have indicated. The last EMA of the day will also include an option for the participants to submit a voice recording, serving as a "daily journal" at the end of the day to understand participant's daily experiences, including daily stressors and mindfulness practice application. To mitigate the risk of recording third-party participant voices, participants in the study will be

instructed to complete the voice recording in a private location and to ensure no other individuals are present or speaking during the recording. Participants will be reminded to pause, stop, or restart the recording if another person enters the space. Participants will also be reminded that the voice recording is optional--they may skip voice recording submission without penalty and still receive compensation. Audio will be downloaded from Expiwell, uploaded to Stronghold, then deleted from Expiwell's storage. The audio housed in Stronghold will be deleted after they are transcribed and vetted for accuracy by study staff. A research assistant will monitor responses to the EMA on a daily basis (including the voice recording, where a transcript will automatically become available through Expiwell's AWS service). Any reportable events that are observed will be reported to the PI, and the PI will be available to meet, if necessary, to review concerns regarding a particular participant or any problems that may arise for participants.

Weekly assessments: During first 4 weeks of intervention period (i.e., Recommended Modules), participants will be asked to complete a survey every week. The survey consists of 2 scales (PHQ-9 and GAD-7) as well as 3 items from interoceptive awareness scale, 3 items from de-centering scale, 3 items from perseverative thinking scale, and 1 item from theory of distress scale. Each survey will take 4-5 minutes, with a total of 16-20 minutes over the 4 week period.

Wearable device: Also during the first 4 weeks of intervention period (i.e., Recommended Modules), data will be collected from a Fitbit from each participant. Data collected include total sleep time, sleep onset latency, REM and non-REM sleep duration, sleep/wake variability, and resting heart rate. Each participant will be mailed a Fitbit from the study team along with a pre-paid return envelope at the enrollment in the study. These devices will be assigned to participants and linked to de-identified study accounts only. Participants will be instructed to wear the Fitbit device daily, before going to bed, for the entire 4-week period. At the end of the intervention, participants will be asked to return the Fitbit using the pre-paid return envelope.

Data analysis: Feasibility, acceptability, and preliminary effects will be assessed using data from the T1, T2, and T3 surveys as well as EMA responses. Qualitative data analysis will also be performed for the exit-interviews and voice recordings to further qualify our findings after transcription and deidentification. Exit interviews will be transcribed using Dedoose (already vetted through OIT), while EMA voice recordings will be transcribed automatically through Expiwell's AWS service. Additionally, recruitment and retention rates, completion of weekly modules, adherence to daily EMA and EMI prompts, weekly session attendance, and other engagement metrics from the application (e.g., frequency of EMI-triggered vs. self-initiated practice use, time spent in modules) will be used to inform study and intervention feasibility.

- 6.3 We will take all reasonable precautions to prevent adverse events to participants. As a meditation-based intervention, a number of actions have been taken to minimize meditation-related risks at different stages of the study. During the pre-enrollment stage, individuals with severe mental

illness that could preclude regular class attendance or impact group participation (i.e., symptomatic, untreated bipolar disorder or a history of psychosis and/or schizophrenia) are excluded from the study. During treatment, meditations are created to be relatively short and interspersed with dyads and reflections to minimize probability of risk. Developing strategies for working with physical and emotional discomfort is also an explicit goal of the program.

No drugs will be administered as part of this study. The only devices used are a) the participant's personal cell phone with the intervention content loaded through the Expiwell app and b) a wearable device Fitbit, which is commercially available and FDA-cleared for general wellness monitoring; it will be used solely to collect sleep and physiological data.

For all assessments and guides used for data collection, please refer to the document named "Compiled measures_GEM.docx".

6.4 A list of all data that and how they will be collected during the study is listed below:

Self-report data on feasibility, acceptability, and preliminary efficacy: Data on feasibility and acceptability as well as preliminary efficacy of the intervention on study outcomes (including mental health, functional impairment, emotion regulation, loneliness, mindfulness, self-compassion, stress, sleep, phone use, overall well-being, etc. – refer to Section 6.2 for full list of scales measured at each time point) will be collected via Qualtrics at baseline, post-intervention, 3-month follow-up, and weekly assessments during the first 4 weeks of intervention period (i.e., Recommended Modules).

EMAs: Daily self-reports on stress, mood, and emotional states will be collected on the Expiwell application. Furthermore, voice recordings for a "daily journal" will be collected during the last EMA of the day. Participants will be reminded that the voice recording is optional--they may skip voice recording submission without penalty and still receive compensation.

App engagement metrics: Frequency and duration of EMI-triggered and self-initiated mindfulness practice sessions will be collected on Expiwell.

Sleep metrics: Continuous objective data on sleep metrics (e.g., sleep latency, REM/non-REM sleep, sleep fragmentation, total sleep time, sleep efficiency) will be collected using wearable devices (i.e., Fitbits).

Semi-structured interviews: Qualitative feedback on intervention experience, feasibility, acceptability, and suggestions for improvement will be collected through a semi-structured Zoom interview with an RA.

6.5 Participants will complete a 3-month post-baseline follow-up survey after the 4-6-week intervention (4 weeks recommended, 2 weeks optional/bonus). Similarly to post-intervention survey, this assessment will collect self-report data on mental health, functional impairment, emotion regulation, loneliness, mindfulness, self-compassion, stress, sleep, phone use, overall well-being, etc. (refer to Section 6.2 for full list of scales measured 3-month follow-up).

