2.0 Objectives

- 2.1 The objectives of this study are to: (a) examine the feasibility, acceptability, and preliminary efficacy of a mindfulness-based, app-delivered intervention to address mental health and emotion regulation challenges experienced by young adults with early life adversities (ELAs); and (b) understand mechanisms of change underlying the intervention, including the role of mindfulness (i.e., interoceptive awareness and de-centering), rumination, and sleep using real-time data collection via ecological momentary assessments (EMAs) and wearable devices.
- 2.2 We hypothesize that young adults will find the Growth, Empowerment, and Mindfulness (GEM) intervention to be both feasible and acceptable, as demonstrated by participants' engagement and quantitative/qualitative feedback; we also hypothesize that the engagement with the intervention will demonstrate preliminary efficacy for improving outcome measures including depression, anxiety, self-compassion, emotion regulation, loneliness, and healthier phone use. We further hypothesize that the mechanisms underlying the benefits of the intervention will be improvements in mindfulness and sleep, as well as reductions in rumination.

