4.0 Study Endpoints

- 4.1 We will collect quantitative and qualitative data from young adults, aged 18-24 (n=44). We will end data collection when the target sample size is reached or when sufficient data is collected to assess feasibility, acceptability, and preliminary efficacy outcomes (whichever comes first).
- 4.2 For safety endpoints, we will monitor for adverse events or any negative effects of the intervention; participants are free to withdraw from the study at any time, in which case their participation will end immediately with no penalty.

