5.0 Study Intervention/Investigational Agent

- 5.1 The Growth, Empowerment, and Mindfulness (GEM) intervention is a structured, mindfulness-based intervention designed to offer support for young adults with early life adversities and their negative behavioral health consequences through

the development of awareness, emotion regulation, and adaptive coping skills. Through psychoeducation content, group practice sessions, and formal and informal mindfulness practices, GEM is aimed at helping participants build foundational mindfulness and self-compassion skills, increase interoceptive awareness, reduce experiential avoidance and de-centering, improve emotion regulation and decrease rumination, and integrate mindfulness skills into daily life. The specific content of the GEM intervention is currently under development with community feedback from relevant Community Advisory Board members (refer to “Intervention_GEM.docx” for drafted scripts of Weeks 1-4 and the Bonus Modules, which will guide the recorded materials; also refer to “Outline_GEM.docx” for intervention outline for each week).

- 5.2 Contents of the GEM intervention is delivered through an existing third-party mobile application (i.e., Expiwell) and consists of 4 weeks of “Recommended Modules” and 2 weeks of “Bonus Modules”. Each week, participants will gain access to a set of 5-11 modules, with each module combining formats of text and audio recordings of psychoeducational content and mindfulness practices. Each week’s modules are further divided into ‘core’ and ‘optional tailored’ modules.

	Recommended Modules (i.e., Weeks 1-4)	Bonus Modules (i.e., Weeks 5-6)
Core modules	Core modules in weeks 1-4 cover topics of early life stress and resilience, environmental stress and disembodied living, experiential avoidance, emotion regulation, mindful self-care, and self-compassion	Core modules in weeks 5-6 cover topics related to media consumption and purpose
Optional tailored modules	Throughout Weeks 1-6, Optional tailored modules will focus on topics of (a) minority stress for participants who identify as a minority member and (b) trauma for participants wanting to receive more information about trauma	

On the application, participants will also have access to a list of all mindfulness exercises that have been taught each week.

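### The adverse-effects scale is given only at T2, so participants who leave before T2, and everyone after T2, have no structured adverse-effects measurement

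*Protocol*

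**What the plan says.** Protocol Section 6.2 describes the programme: "The intervention will include 4 weeks of Recommended Modules followed by 2 weeks of Bonus Modules that participants can opt to complete". It places T2 relative to the recommended part: "The post-intervention assessment (T2) will take place 1-2 weeks after the recommended modules are completed". T3 is three months after baseline.

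The T2 list of 26 scales closes with "applied mindfulness process, overall well-being, client satisfaction, session evaluation, and adverse effects". The T3 list closes with "perceived stress, political stress, sleep, phone use, applied mindfulness process, and overall well-being" and contains no adverse-effects scale. The baseline list has none either. The weekly survey in Weeks 1-4 holds PHQ-9, GAD-7 and ten single items on mechanisms.

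Section 4.2 states the safety endpoint in general terms: "we will monitor for adverse events or any negative effects of the intervention". It gives no instrument or schedule. Section 14.2 provides a debrief at withdrawal without naming any harms questions. The SAP contains no analysis of harms.

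On phone use, Section 2.2 lists the hypothesised improvements as "depression, anxiety, self-compassion, emotion regulation, loneliness, and healthier phone use". The module table in Section 5.2 says "Core modules in weeks 5-6 cover topics related to media consumption and purpose".

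**The concern.** The adverse-effects scale is the only listed measure dedicated to unwanted effects. Given once, at T2, it reaches only people still in the study and only covers the time up to T2. Leaving may be related to harm: Section 14.1 makes psychosis and imminent suicidal risk grounds for withdrawal, and a participant distressed by meditation may simply stop. A harms rate among T2 completers could then understate the rate among all who started.

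Exposure can also continue after the scale is given. A T2 one week after Week 4 leaves a bonus week to run, and Section 5.2 offers the optional trauma modules throughout Weeks 1-6, whereas EMA and the weekly surveys stop after Week 4. A feasibility trial meant to inform later studies should give a harms figure with a clear denominator.

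**Working it through.** **1. The plan's own figures.** 35/44 = 79.5%, which agrees with the approximately 80% in Section 12.2. Counting the lists in Section 6.2 gives 27 scales at T1 (27 stated), 26 at T2 (26 stated) and 23 at T3 (21 stated). The T3 discrepancy does not matter here: the list is longer than the stated count, so the count does not suggest that an adverse-effects scale was left off.

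**2. Timing.** Recommended modules end at Week 4. T2 is at 4 + 1 = Week 5 to 4 + 2 = Week 6. Bonus time still to run at T2 is 6 − 5 = 1 week at the early edge and 6 − 6 = 0 at the late edge. Taking T3 as about Week 13 after baseline and assuming that modules start at baseline, the time from T2 to T3 is 13 − 6 = 7 to 13 − 5 = 8 weeks. If modules start 1 to 4 weeks after baseline (assumed range), it is 3 to 7 weeks.

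**3. How many are never given the scale.** The SAP asks for more than 70% to complete T2. 30/44 = 68.2% fails and 31/44 = 70.5% passes, so a trial that meets its benchmark can leave up to 44 − 31 = 13 (29.5%) unasked. Section 12.2 aims for at least 35 who complete everything, follow-up included, so at least 35 reach T2 and at most 44 − 35 = 9 (20.5%) are unasked.

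**4. Which harms other measures reach.** Section 15.1 lists the more common effects. Set against the measures in Section 6.2:

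- Depression and anxiety: PHQ-9 and GAD-7 weekly in Weeks 1-4; depression and anxiety scales and both MINI modules at T1, T2 and T3.
- Re-experiencing of trauma: PTSD scale at T1, T2 and T3.
- Insomnia: sleep scale at T1, T2 and T3; Fitbit in Weeks 1-4.
- Suicidality, among the rarer serious effects: reviewed at screening, T1, T2 and T3 (Section 18.1).
- Dissociation, executive dysfunction, headaches and body pain: named by no listed measure. The content of the adverse-effects scale itself is in a separate file that is not available here.

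**5. Possible bias.** With n T2 completers, harm rate p in completers and q in leavers, the rate over all enrolled is [n·p + (44 − n)·q]/44, while the reported rate is p. Taking p = 10% (assumed):

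| q (assumed) | n = 35 | n = 31 |
|---|---|---|
| 0% | 3.5/44 = 8.0% | 3.1/44 = 7.0% |
| 10% | 10.0% | 10.0% |
| 20% | 5.3/44 = 12.0% | 5.7/44 = 13.0% |
| 30% | 6.2/44 = 14.1% | 7.0/44 = 15.9% |
| 50% | 8.0/44 = 18.2% | 9.6/44 = 21.8% |

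**6. If no harms are reported.** The one-sided 95% upper limit is 1 − 0.05^(1/n): 9.2% for n = 31, 8.2% for n = 35 and 6.6% for n = 44. The last is a best case that needs every leaver to be reached. With no assumption about leavers, zero harms in 31 is compatible with 0 to 13/44 = 29.5% of those enrolled, and zero in 35 with 0 to 9/44 = 20.5%.

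**The case against.** The strongest reply is that safety does not rest on this one scale. Section 4.2 does not define the endpoint as the T2 scale. Weekly PHQ-9 and GAD-7 also cover people who leave later. EMA asks about mood and stress three times a day and is reviewed daily, so it is solicited information. Symptom, MINI and suicidality measures continue to T3, participants are encouraged to report distress, and partial withdrawers are still invited to the exit interview. This stands. A reader might infer that harms in dropouts and after T2 are simply missed; the documents do not support that. What remains is narrower: effects that no other measure names, and any question to the participant about unwanted effects of the programme, for those who miss T2 and for everyone afterwards.

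A reader might also infer that T2 is mistimed and should move, or that the phone-use hypothesis cannot be tested. Neither follows. T2 is anchored to the recommended four-week course, as are EMA, the weekly surveys, the group sessions and the SAP's audio benchmark. The bonus weeks are optional, so exposure to them would vary at any T2 date. Phone use is measured again at T3, which on the nominal schedule follows the bonus content. The SAP prespecifies no T1-T2 phone-use test, and the link between the media-consumption modules and the phone-use scale is an inference.

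Finally, the bias figures depend on assumed rates, and some leavers will be out of reach of any debrief. Both points are accepted, which is why step 5 gives a range and the 6.6% limit is called a best case.

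**Conclusion.** The gap is real, limited and cheap to close. The adverse-effects scale is listed at T2 only, and T2 can precede the end of the bonus weeks. Up to 13 of 44 participants (29.5%) if the retention benchmark is just met, or at most 9 (20.5%) at the protocol's target, would have no structured adverse-effects measurement; nor would anyone after T2. The counts follow from the documents. Any bias does not: it is zero if leavers and completers have equal harm rates, and 4.1 or 5.9 percentage points (35 or 31 completers) under the assumed 10% and 30%. The finding relies on the measure lists in Section 6.2, since the compiled measures file could not be checked. Phone use supports a reporting note only: T1-T2 change may not reflect the full bonus content.

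**What to change.** 1. Give the existing adverse-effects scale at the Section 14.2 withdrawal debrief, where the participant can be reached, and at T3.
2. Add a short harms paragraph to the SAP: report harms with all enrolled as the reference, by time point, and state the number never asked. Show any adjustment for leavers as a range over assumed rates, not as one figure.
3. Leave the timing of T2 unchanged. As a reporting note, interpret phone use at T3 and report from the app logs how many bonus modules each participant had completed before T2.

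The cost is a few minutes for the participant at each of two existing contacts, plus a few sentences in the SAP. No new instrument or visit is needed. People lost to all contact will still be unasked, and the reported count makes that visible.
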